3.2 Drug Administration

3.2.1 Trametinib

Trametinib will be given orally at designated dose once a day on every day of every 28-day cycle.

Trametinib should be taken orally at least 1 hour before and 2 hours after a meal with approximately 200 mL of water. If a subject vomits after taking study treatment, the subject should be instructed not to retake the dose but should be instructed to take the next scheduled dose. If a subject misses a dose of trametinib, the subject may take the dose immediately if the next dose is scheduled for at least 12 hours later. If the next scheduled dose is due in less than 12 hours, the subject should skip the dose and resume dosing at the next scheduled dose.

Missing of 20% of the doses for any given cycle is allowed.

Patients will complete and return Patient's Diary ([Appendix C](#)).

3.2.2 Hydroxychloroquine (HCQ)

Hydroxychloroquine will be given orally at designated dose twice a day on every day of every 28-day cycle.

Hydroxychloroquine should be taken at approximately the same times each day. Doses should be taken within 2 hours of the scheduled time.

In case of a missed dose (more than 2 hours late) or vomiting after taking hydroxychloroquine, patients will be instructed not to make up the missed dose.

Hydroxychloroquine will be taken orally with a meal or a glass of milk.

Missing of 20% of the doses for any given cycle is allowed.

Patients will complete and return Patient's Diary ([Appendix C](#)).

3.3 Dose Modifications/Delay

In case of unbearable toxicity definitely attributed to one of the study drugs, patient will be taken off this drug and per PI discretion may continue treatment with the other drug only.

When, at the beginning of a treatment cycle, treatment delay related to one of the drugs is indicated, both study drugs should be held and resumed concurrently.

If, in the opinion of the investigator, a toxicity is considered to be due solely to one drug, the dose of the other drug may not require modification per PI discretion.

Dose interruptions for study treatment-related AEs are allowed as per the dose modification recommendations. Doses of any investigational product that were not administered due to toxicity will not be replaced within the same cycle. In addition to dose interruption, the need for a dose reduction at the time of treatment resumption should also be considered based on the dose modifications recommendations. If a toxicity-related dose delay of HCQ and trametinib for >28 days is required, treatment will be discontinued permanently, and the patient should be removed from study treatment.

3.3.1 Dose reduction

Following dosing interruption due to treatment related toxicity, the offending agent may need to be resumed at a reduced dose as per the dose modification recommendations as following. Dose

reduction should proceed by decreasing the administered dose by 0.5 mg of original dose of trametinib or 400 mg of original dose of HCQ.

3.3.2 Hydroxychloroquine

Table 4 Guidelines for hydroxychloroquine-related toxicities

Adverse Event	1 st Occurrence	2 nd Occurrence
Hematology Grade 4 neutropenia lasting \geq 7 consecutive days Grade 4 thrombocytopenia \geq 7 consecutive days Grade \geq 3 neutropenia with fever (temperature \geq 38.5 °C)	Hold HCQ and trametinib. Continue weekly hematologic monitoring. Once AE resolves to \leq Grade 1, restart study drugs, with HCQ at next lower dose level.	Discontinue HCQ and trametinib
Skin and subcutaneous tissue disorders Grade \geq 3 rash, hand-foot skin reaction or photosensitivity lasting $>$ 7 consecutive days despite skin toxicity treatment	See Table 5	Discontinue HCQ and trametinib
Eye disorders Grade 2 retinal events lasting $>$ 14 consecutive days confirmed by ophthalmologic examination Grade \geq 3 retinal events confirmed by ophthalmologic examination	Hold HCQ and trametinib. Monitor until AE resolves to Grade \leq 1. Patients should be referred for ophthalmologic exam. Restart study drugs, with HCQ at next lower dose level.	Discontinue HCQ and trametinib
Gastrointestinal Grade \geq 3 nausea or vomiting lasting \geq 7 days despite optimal anti-emetic therapy	Hold HCQ and trametinib. Monitor until AE resolves to Grade \leq 1. Restart study drugs, with HCQ at next lower dose level.	Discontinue HCQ and trametinib
Grade \geq 3 diarrhea lasting \geq 7 days despite optimal anti-diarrhea treatment	See Table 6	Discontinue HCQ and trametinib
Hepato-biliary Grade \geq 3 total bilirubin felt to be not related to progression of disease Grade \geq 3 ALT (isolated increases in AST without concomitant increases in ALT will not be considered dose-limiting because of the non-specific nature of AST) Grade 4 alkaline phosphatase lasting \geq 7 consecutive days felt to be not related to progression of disease	Hold HCQ and trametinib. Monitor with weekly CMP until AE resolves to Grade \leq 1. Restart study drugs, with HCQ at next lower dose level.	Discontinue HCQ and trametinib
ECG QT Interval	Hold HCQ and trametinib. Monitor	Discontinue HCQ

Abbreviated Title: Trametinib and HCQ in BTC**Version Date: 04/06/2022**

Adverse Event	1 st Occurrence	2 nd Occurrence
QTcF interval \geq 501 ms on at least two separate ECGs	with ECG until AE resolves to Grade \leq 1. Restart study drugs, with HCQ at next lower dose level.	and trametinib
Renal Serum creatinine \geq Grade 2	Check cystatin-C levels. If GFR calculated by cystatin C is \geq 30 mL/min/1.73 m ² , continue HCQ and trametinib. If GFR calculated by cystatin C is \leq 30 mL/min/1.73 m ² , hold HCQ and trametinib. Monitor with weekly CMP and cystatin C until AE resolves to \leq Grade 1. Restart study drugs, with HCQ at next lower dose level.	Check cystatin-C levels. If GFR calculated by cystatin C is \geq 30 mL/min/1.73 m ² , continue HCQ and trametinib. If GFR calculated by cystatin C is \leq 30 mL/min/1.73 m ² , discontinue HCQ and trametinib.* *2nd occurrence of elevated serum creatinine will only be determined if 1st occurrence included elevated cystatin C and dose reduction.
Hypoglycemia	Hold HCQ if Grade 2. Monitor AE until resolution to Grade \leq 1. Restart study drugs, with HCQ at next lower dose level. Hold HCQ if Grade 3. Monitor AE until resolution to Grade \leq 1. Restart study drugs HCQ at next lower dose level. Discontinue HCQ permanently if Grade 4	Discontinue HCQ and trametinib
Non-hematologic events Grade \geq 3, except for the exclusions noted below: • Grade 3 alopecia • < 5 days of Grade 3 fatigue • < 5 days of Grade 3 edema • Grade 3 laboratory abnormalities that are responsive to oral supplementation	Hold HCQ and trametinib. Monitor AE until resolution to Grade \leq 1. Restart study drugs, with HCQ at next lower dose level.	Discontinue HCQ and trametinib

Adverse Event	1 st Occurrence	2 nd Occurrence
or deemed by the investigator to be clinically insignificant		

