3.3.3 Trametinib

Dose reductions for adverse reactions associated with trametinib are presented in **Table 5**

Table 5: Recommended Dose Reductions for Trametinib for Adverse Reactions

Action	Recommended Dose
First Dose Reduction	1.5 mg orally once daily
Second Dose Reduction	1 mg orally once daily
Subsequent Modification	Permanently discontinue if unable to tolerate trametinib 1 mg orally once daily

Dosage modifications for adverse reactions associated with trametinib are presented in **Table 6**.

Table 6 Recommended Dosage Modifications for Trametinib for Adverse Reactions

Severity of Adverse Reaction ^a	Dosage Modification for Trametinib ^b
Venous Thromboembolism	
Uncomplicated deep venous thrombosis (DVT) or pulmonary embolism (PE)	Withhold trametinib for up to 3 weeks. 
• If improved to Grade 0-1, resume trametinib at lower dose.• If not improved, permanently discontinue trametinib.
Life threatening PE	
Cardiomyopathy	Permanently discontinue trametinib.
Asymptomatic, absolute decrease in left ventricular ejection fraction (LVEF) of 10% or greater from baseline and is below institutional lower limit of normal (LLN) from pretreatment value	Withhold trametinib for up to 4 weeks. 
• If improved to normal LVEF value, resume trametinib at lower dose.• If not improved to normal LVEF value, permanently discontinue

Severity of Adverse Reaction^a	Dosage Modification for Trametinib ^b
	trametinib.
Symptomatic cardiomyopathy Absolute decrease in LVEF of greater than 20% from baseline that is below LLN	Permanently discontinue trametinib.
Ocular Toxicities	
Retinal pigment epithelial detachments (RPED)	Withhold trametinib for up to 3 weeks. 
• If improved, resume trametinib at same or lower dose.• If not improved, permanently discontinue trametinib or resume trametinib at lower dose.
Retinal vein occlusion (RVO)	Permanently discontinue trametinib.
Pulmonary	
Interstitial lung disease (ILD)/pneumonitis	Permanently discontinue trametinib.
Febrile Reactions	
Fever higher than 104°F Fever complicated by rigors, hypotension, dehydration, or renal failure	Withhold trametinib until fever resolves, then resume trametinib at same or lower dose.
Skin Toxicities	

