Intolerable Grade 2 Grade 3 or 4	Withhold trametinib for up to 3 weeks. 
• If improved, resume trametinib at lower dose.• If not improved, permanently discontinue.
Severe cutaneous adverse reactions (SCARs)	Permanently discontinue trametinib.
Other Adverse Reactions, including Hemorrhage	

Severity of Adverse Reaction^a	Dosage Modification for Trametinib ^b
Intolerable Grade 2	Withhold trametinib
Any Grade 3	
• If improved to Grade 0-1, resume at lower dose.• If not improved, permanently discontinue.
First occurrence of any Grade 4	
• Withhold trametinib until improves to Grade 0-1, then resume at lower dose. 
Or
 
• Permanently discontinue trametinib.
Recurrent Grade 4	Permanently discontinue trametinib.

^a National Cancer Institute Common Terminology Criteria for Adverse Events (NCI CTCAE) version 5.0.

^b See **Table 5** for recommended dose reductions of trametinib.

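### Table 4 sends a first persistent Grade ≥3 HCQ-related rash or diarrhea to trametinib-only tables, while its general row gives a different instruction and nothing says which governs

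*Combined protocol and SAP*

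**What the plan says.** Section 3.3.2 presents Table 4 as "Guidelines for hydroxychloroquine-related toxicities". Most of its rows state the first-occurrence HCQ action in the cell itself: hold, wait for recovery, resume with HCQ reduced. Two rows do not.

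- Skin: Grade ≥3 rash, hand-foot skin reaction or photosensitivity lasting more than 7 "consecutive days despite skin toxicity treatment". The first-occurrence cell only refers to Table 5.
- Diarrhea: Grade ≥3, lasting at least 7 "days despite optimal anti-diarrhea treatment". The first-occurrence cell only refers to Table 6.

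In both rows the second occurrence stops both drugs.

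Table 5 in section 3.3.3 is titled "Recommended Dose Reductions for Trametinib for Adverse Reactions" and is a ladder of trametinib doses. Table 6 is titled "Recommended Dosage Modifications for Trametinib for Adverse Reactions". It has a skin row ("Intolerable Grade 2 Grade 3 or 4") and a group for other adverse reactions, into which diarrhea falls. Neither table mentions HCQ.

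The last row of Table 4 covers Grade ≥3 non-hematologic events without a minimum duration, and its listed exclusions include neither rash nor diarrhea. Its first-occurrence instruction begins "Hold HCQ and trametinib. Monitor AE until resolution to Grade" 1 or lower, and it restarts with HCQ one level down.

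**The concern.** A table for HCQ-related toxicity should tell the investigator what to do with HCQ. For these two events the specific cell leads only to changes in the other drug, while another row of the same table gives an HCQ instruction for what is, as worded, the same event. Two investigators could read the table in good faith and dose like patients differently.

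This also does not fit section 1.2.7, which plans to lower HCQ for effects specific to HCQ and to hold trametinib at its standard dose unless the effect is specific to trametinib.

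What is at stake is patient dosing and the tolerability result, which is a secondary objective. The same toxicities, at the same durations, appear among the dose-limiting toxicities in section 3.1.1. Section 3.1.2 refers patients who continue after such a toxicity to section 3.3, so run-in patients can meet these rows. If HCQ was not lowered after the first event, a recurrence costs the patient both drugs.

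**Working it through.** The check is mainly a comparison of rows. The plan gives no figure to reproduce.

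Inputs: starting doses of trametinib 2 mg once daily and HCQ 600 mg twice daily (section 3.1); reduction steps of 0.5 mg and 400 mg (section 3.3.1); a 28-day limit on a toxicity-related delay of both drugs (section 3.3); Tables 4, 5 and 6.

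Size of one step:

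- HCQ: 2 × 600 = 1,200 mg daily; 1,200 − 400 = 800 mg; 400/1,200 = 33% lower.
- Trametinib: 2 − 0.5 = 1.5 mg; 0.5/2 = 25% lower.

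First HCQ-related event, by the row followed:

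| Event and row | Hold | Trametinib | HCQ |
|---|---|---|---|
| Rash >7 days, specific row via Table 5 | none stated | dose ladder, first step 1.5 mg | none stated |
| Rash >7 days, if Table 6 was meant | trametinib, up to 3 weeks (21 days) | resumed lower if improved | none stated |
| Diarrhea ≥7 days, specific row via Table 6 (Grade 3) | trametinib | resumed lower at Grade 0-1 | none stated |
| Either of these, general row of Table 4 | both drugs, to Grade ≤1, within the 28-day limit | restarted, no reduction stated | one level lower, 800 mg |
| Rash ≤7 days or diarrhea <7 days (general row only) | both drugs, as above | restarted, no reduction stated | one level lower, 800 mg |

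There are two ways to read Table 4.

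1. Both rows apply. A persistent event then has two instructions that differ in which drug is held and which is reduced.
2. The specific row overrides the general one. The persistent event then has no stated HCQ action, while the shorter event brings a hold and a 33% HCQ reduction.

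The plan does not say which reading holds, and each leaves a defect. Correcting a possible misnumbering of Table 5 as Table 6 does not help, because the Table 6 skin row also acts on trametinib alone.

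Sections 3.3 and 3.3.1 do not supply the missing step. Section 3.3 requires both drugs to be held together only for a delay at the start of a cycle, and its discretion clause concerns the drug not held responsible. Section 3.3.1 gives the size of an HCQ step but leaves its use to the tables.

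**The case against.** The strongest defence is clinical. Rash and diarrhea are prominent trametinib toxicities: in the melanoma trial summarised in section 1.2.5, skin toxicity of any kind occurred in 87% and severe skin toxicity in 12% of trametinib patients, and Table 1 gives rash in 57% and diarrhea in 43%. The HCQ section (1.2.6.2) lists neither diarrhea nor general rash. Sending these two rows to the trametinib tables may therefore be deliberate management by likely culprit, and an event truly due to HCQ may be uncommon. The tables are offered as guidelines and recommendations, the team discusses each patient weekly, and section 3.3 removes a drug that is definitely responsible for unbearable toxicity. All of this stands and limits the weight of the point. It does not explain why an event already classed as HCQ-related has no HCQ instruction in its own row.

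Three stronger readings are tempting, and the documents do not support them.

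- A reader might infer that persistent events certainly escape any HCQ action. That follows only if the specific row overrides the general one; as worded, the general row covers them too.
- A reader might infer that section 3.3.1 is breached. Its wording on the offending agent is permissive and defers to the tables, so there is no rule to breach.
- A reader might infer a separate conflict for hypoglycemia, whose own row says "Discontinue HCQ permanently if Grade 4" while the general row restarts HCQ lower. If specific rows govern, no conflict exists. If they do not, it is another instance of the missing precedence rule.

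**Conclusion.** The point holds as a minor safety-management correction. For a first persistent Grade ≥3 rash or diarrhea attributed to HCQ, Table 4 either gives two different instructions or gives none for HCQ, depending on a precedence rule that the plan does not state.

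Per event, the HCQ difference is between no stated change and a hold followed by a reduction from 1,200 to 800 mg daily. It is limited to the first occurrence, since a second stops both drugs, and an investigator may still act on HCQ by judgment.

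Frequency cannot be estimated. The 3 of 25 patients with Grade 3 rash in Table 3 received a triplet that included dabrafenib, and the table gives neither duration nor attribution to HCQ. Sample size, the two-stage decision rule and error rates are unaffected.

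The conclusion assumes only that Table 4 applies to events attributed to HCQ, as its title says.

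**What to change.** 1. In the skin and diarrhea rows of Table 4, replace the cross-reference with an instruction split by attribution.
   - Attributed to HCQ: hold both drugs until the event is Grade 1 or lower, then resume with HCQ reduced by one level, as neighbouring rows already provide.
   - Attributed to trametinib: follow Table 6, using its skin row for rash and its other-reactions rows for diarrhea.
   - Attributed to both: hold both, apply the stricter restart and discontinuation criterion, and leave the choice of which drug to reduce to the principal investigator, in keeping with section 3.3. For skin, recovery to Grade ≤1 is stricter than improvement alone, and the three-week limit in Table 6 is stricter than 28 days. Naming the stricter criterion avoids setting the two tables against each other.
2. Limit the general row to Grade ≥3 non-hematologic events that do not meet the criteria, including duration, of a row above it. Shorter rash and diarrhea stay covered by it, and Grade 4 hypoglycemia clearly follows its own row.

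The cost is an edit to three rows of Table 4 (skin, diarrhea, general) in the next amendment. The investigators need to agree the rule for events attributed to both drugs. No visits, procedures or patients are added.

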1.2.5.2 Toxicity

Cardiomyopathy

METRIC clinical trial is an international multicenter randomized (2:1), open-label, active-controlled trial in 322 patients with BRAF V600 E or V600 K mutation-positive, unresectable or metastatic melanoma trial. Cardiomyopathy [defined as cardiac failure, left ventricular dysfunction, or decreased left ventricular ejection fraction (LVEF)] occurred in 7% (14/211) of patients treated with trametinib; no chemotherapy-treated patient in Trial 1 developed cardiomyopathy. The median time to onset of cardiomyopathy in patients treated with trametinib was 63 days (range 16 to 156 days); cardiomyopathy was identified within the first month of treatment with trametinib in five of these 14 patients. Four percent of patients in METRIC trial required discontinuation (4/211) and/or dose reduction (7/211) of trametinib. Cardiomyopathy resolved in 10 of these 14 (71%) patients.

Across clinical trials of trametinib at the recommended dose (N = 329), 11% of patients developed evidence of cardiomyopathy (decrease in LVEF below institutional lower limits of normal with an absolute decrease in LVEF $\geq 10\%$ below baseline) and 5% demonstrated a decrease in LVEF below institutional lower limits of normal with an absolute decrease in LVEF of $\geq 20\%$ below baseline. Assess LVEF by echocardiogram or multigated acquisition (MUGA) scan before initiation of trametinib, one month after initiation of trametinib, and then at 2- to 3-month intervals while on treatment. Withhold treatment if absolute LVEF value decreases by 10% from pre-treatment values and is less than the lower limit of normal. Permanently discontinue trametinib for symptomatic cardiomyopathy or persistent, asymptomatic LVEF dysfunction that does not resolve within 4 weeks.

Retinal pigment Epithelial Detachment (RPED)

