^aEvents included are higher in the trametinib arm compared with chemotherapy by $\geq 5\%$ in 141 overall incidence or by $\geq 2\%$ Grade 3-4 adverse reactions higher in trametinib arm compared 142 with chemotherapy.

^bNational Cancer Institute Common Terminology Criteria for Adverse Events, version 4.0.

^cGrade 4 adverse reactions were limited to rash (n = 1) in trametinib arm and diarrhea (n = 1) in the chemotherapy arm.

^dIncludes the following terms: stomatitis, aphthous stomatitis, mouth ulceration, and mucosal inflammation.

^eIncludes the following terms: abdominal pain, abdominal pain lower, abdominal pain upper, and abdominal tenderness.

^fIncludes the following terms: lymphedema, edema, and peripheral edema.

^gIncludes the following terms: epistaxis, gingival bleeding, hematochezia, rectal hemorrhage, melena, vaginal hemorrhage, hemorrhoidal hemorrhage, hematuria, and conjunctival hemorrhage.

Other clinically important adverse reactions observed in $\leq 10\%$ of patients (N = 329) receiving trametinib were: bradycardia, dry mouth, folliculitis, rash pustular, cellulitis, rhabdomyolysis, dizziness, dysgeusia, blurred vision, dry eye

Table 2. Laboratory Abnormalities Occurring at a Higher Incidence in Patients Treated with Trametinib in the METRIC Study [Between-arm Difference of $\geq 5\%$ (All Grades) or $\geq 2\%$ (Grades 3 or 4)^a]

Laboratory Abnormality	Trametinib N = 211		Chemotherapy N = 99	
	All Grades	Grades 3 and 4	All Grades	Grades 3 and 4
Increased aspartate aminotransferase (AST)	60	2	16	1
Hypoalbuminemia	42	2	23	1
Increased alanine aminotransferase (ALT)	39	3	20	3
Anemia	38	2	26	3
Increased alkaline phosphatase	24	2	18	3

^aOnly grade 3 adverse reactions were reported in either treatment arm

Further information on these risks (e.g. presenting symptoms) can be found in the current version of the trametinib package insert.

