Post marketing cases of life-threatening and fatal cardiomyopathy have been reported with use of HCQ as well as with use of chloroquine. Patients may present with atrioventricular block, pulmonary hypertension, sick sinus syndrome or with cardiac complications. ECG findings may include atrioventricular, right or left bundle branch block. Signs or symptoms of cardiac compromise have appeared during acute and chronic treatment. Clinical monitoring for signs and symptoms of cardiomyopathy is advised, including use of appropriate diagnostic tools such as ECG to monitor patients for cardiomyopathy during HCQ therapy. Chronic toxicity should be considered when conduction disorders (bundle branch block/atrio-ventricular heart block) or biventricular hypertrophy are diagnosed. If cardiotoxicity is suspected, prompt discontinuation of HCQ may prevent life-threatening complications. HCQ prolongs the QT interval. Ventricular arrhythmias and torsade's de pointes have been reported in patients taking HCQ. Therefore, HCQ should not be administered with other drugs that have the potential to prolong the QT interval

Worsening of psoriasis and porphyria:

Use of HCQ in patients with psoriasis may precipitate a severe attack of psoriasis. When used in patients with porphyria the condition may be exacerbated. The preparation should not be used in these conditions unless in the judgment of the physician the benefit to the patient outweighs the possible hazard.

Proximal Myopathy and Neuropathy:

Skeletal muscle myopathy or neuropathy leading to progressive weakness and atrophy of proximal muscle groups, depressed tendon reflexes, and abnormal nerve conduction, have been reported. Muscle and nerve biopsies have been associated with curvilinear bodies and muscle fiber atrophy with vacuolar changes. Assess muscle strength and deep tendon reflexes periodically in patients on long-term therapy with HCQ.

Neuropsychiatric events, including suicidality:

Suicidal behavior has been rarely reported in patients treated with HCQ.

Hypoglycemia:

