1.2.6.3 Toxicities of the combination of trametinib and HCQ

There is no data available in terms of this combination though there should have this information accessible in the near future since several trials involved with this combination is ongoing. However, there is safety data from the BAMM trial (NCT02257424), that is designed for patients with advanced BRAF mutant melanoma treated with dabrafenib, trametinib, and hydroxychloroquine. The doses of trametinib and hydroxychloroquine used in the BAMM trial is the exact same as we plan in our trial except that we are not planning BRAF inhibitor dabrafenib. Therefore, this precious data will provide important reference for our trial. From personal communication with [name] (Primary Investigator of BAMM trial, University of Pennsylvania), we summarize the safety profile from BAMM trial as showed in the following **Table 3**.

Table 3. Safety profile in the BAMM Study

Adverse Event	Dabrafenib + trametinib + HCQ (BAMM)	
	Grade 1-2	Grade 3
Chills	14 (56%)	1 (4%)
Diarrhea	13 (52%)	0
Fever	13 (52%)	1 (4%)
Nausea	12 (48%)	1 (4%)
Fatigue	11 (44%)	0
Headache	9 (36%)	0
Myalgia	9 (36%)	0
Rash	9 (36%)	3 (12%)
Anorexia	8 (32%)	0
Dry mouth	7 (28%)	0
Pruritus	7 (28%)	0
Arthralgia	6 (24%)	0
Abdominal pain	5 (20%)	0
Vomiting	5 (20%)	0
Constipation	4 (16%)	0
Dysgeusia	4 (16%)	0
Creatinine increased	3 (12%)	0
Dehydration	3 (12%)	2 (8%)
QTc prolonged	3 (12%)	1 (4%)
Increased alanine aminotransferase	1 (4%)	2 (8%)
Ejection fraction decreased	0	1 (4%)

With the triplet combination, the most common adverse effects are chills, diarrhea, fever, nausea, rash, and fatigue with grade 1-2. No grade 4 AEs are reported. This information indicates the less adverse effects we foresee with trametinib and hydroxychloroquine in our trial.

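### For a toxicity attributed to both drugs, Table 4 restarts trametinib after recovery where Table 6 stops it for good, and nothing says which table governs

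*Combined protocol and SAP*

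**What the plan says.** Table 4 (section 3.3.2) is headed as guidance for hydroxychloroquine (HCQ) toxicities, but most of its cells direct both drugs. The catch-all row for Grade ≥3 non-hematologic events and the eye row for retinal events hold both drugs until Grade ≤1 and then say: "Restart study drugs, with HCQ at next lower dose level". At a second occurrence both drugs stop.

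Table 6 (section 3.3.3) covers reactions associated with trametinib. It stops trametinib permanently for symptomatic cardiomyopathy, an LVEF fall of more than 20% from baseline to below the lower limit of normal (LLN), retinal vein occlusion (RVO), and interstitial lung disease (ILD) or pneumonitis. Section 1.2.5.2 repeats the cardiac rule: "Permanently discontinue trametinib for symptomatic cardiomyopathy or persistent, asymptomatic LVEF dysfunction that does not resolve within 4 weeks". It also gives the permanent stops for RVO and for treatment-related ILD or pneumonitis.

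On attribution, section 3.3 lets the PI leave the second drug alone when one drug is to blame: "If, in the opinion of the investigator, a toxicity is considered to be due solely to one drug, the dose of the other drug" may stay as it is. A companion rule covers toxicity definitely attributed to one drug. Section 3.3 also has general rules for treatment-related events: interruptions are allowed, a reduction at resumption is to be considered, and treatment ends if a delay of both drugs exceeds 28 days. Section 3.3.1 says the agent responsible may need a lower dose.

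**The concern.** The two tables overlap when an event is judged related to both drugs. Shared attribution is expected by the plan: section 3.1.1 defines dose-limiting toxicities by attribution to the combination, and section 3.1.2 sends patients who continue after one to section 3.3 for interruption or reduction.

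Cardiomyopathy is the clearest case. It is a listed trametinib risk (section 1.2.5.2), and for HCQ section 1.2.6.2 states: "Post marketing cases of life-threatening and fatal cardiomyopathy have been reported with use of HCQ as well as with use of chloroquine". At stake is patient safety. Read literally, one table puts a recovered patient back on a drug that the other table bars for good.

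**Working it through.** No sample-size or error-rate formula applies. The check sets the tables side by side for an event attributed to both drugs, with trametinib starting at 2 mg daily (section 3.1). Reduction steps are 0.5 mg for trametinib and 400 mg for HCQ (section 3.3.1; Table 5 for trametinib).

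| Event, attributed to both drugs | Trametinib under Table 4 | Trametinib under Tables 5 and 6 | Can both be followed? |
|---|---|---|---|
| Symptomatic cardiomyopathy, or LVEF fall >20% to below LLN; Grade ≥3, recovered to Grade ≤1 | Restart, dose not stated (catch-all row) | 0 mg, permanent | No |
| RVO, Grade ≥3, recovered | Restart, dose not stated (eye row) | 0 mg, permanent | No |
| ILD or pneumonitis, Grade ≥3, recovered | Restart, dose not stated (catch-all row) | 0 mg, permanent | No |
| Other first Grade 3 (for example raised ALT), recovered | Restart, dose not stated | 2 − 0.5 = 1.5 mg | Yes |
| Second Grade 3 after one reduction | 0 mg | 2 − 0.5 − 0.5 = 1 mg | No; Table 4 is the more cautious |
| Recurrent Grade 4 | 0 mg | 0 mg | Yes, they agree |

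Where Table 4 restarts treatment, HCQ goes from 1,200 to 1,200 − 400 = 800 mg/day.

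**Is there a tie-breaker?**
- Section 3.3, attribution rules: they apply only when one drug is responsible.
- Section 3.3, general rules: considering a reduction at resumption refers back to the same recommendations. The 28-day rule removes the conflict only when recovery takes longer than 28 days.
- Section 3.3.1: it concerns a reduced dose and does not address a permanent stop.
- Section 1.2.6.2: "If cardiotoxicity is suspected, prompt discontinuation of HCQ may prevent life-threatening complications". This bears on HCQ and leaves trametinib open.

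None of these says which table directs trametinib when both drugs are implicated.

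**Can the conditions be met?** On trametinib alone, cardiomyopathy occurred in 14/211 = 6.6% (given as 7%), and "Cardiomyopathy resolved in 10 of these 14 (71%) patients" (10/14 = 0.71). Grade, symptoms and time to recovery are not given for those ten. Table 3 shows one patient (4%) with a Grade 3 fall in ejection fraction on dabrafenib plus trametinib plus HCQ. Recovery is therefore possible, and a Grade 3 cardiac event has been seen with both drugs on board. None of these figures gives the rate of a recovered Grade ≥3 event attributed to both drugs, so no probability is computed.

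**Skin row.** For a first occurrence, Table 4 refers to Table 5, which contains only the steps 1.5 mg, 1 mg and stop. The instructions for skin toxicity (how long to withhold, when to resume, when to stop) are in Table 6. The diarrhea row of Table 4 does point to Table 6.

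**The case against.** The best defence is that each table belongs to its own drug, and that a named row should prevail over a catch-all. Symptomatic cardiomyopathy has a named stop in Table 6, repeated in section 1.2.5.2, and section 1.2.6.2 points towards stopping HCQ as well. Tables 4 to 6 are titled as guidelines or recommendations. The collision also needs shared attribution, Grade ≥3, and recovery before the 28-day limit.

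Much of this stands. A careful investigator would probably stop trametinib, and the situation is narrow. But Table 4's cells direct trametinib explicitly, so the table is not confined to HCQ. Its eye row is itself a named row, so preferring the specific to the general does not clearly settle RVO. The protocol never states the precedence that the defence relies on.

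Two stronger readings are tempting and are not supported:
- *That Table 4 orders full-dose trametinib after any first Grade 3 event, against 1.5 mg in Table 6.* Table 4 states no trametinib dose. Lowering HCQ one level under Table 4 and giving trametinib 1.5 mg under Tables 5 and 6 obeys both, and sections 3.3 and 3.3.1 fit that reading. This holds for raised ALT too.
- *That section 3.3 deals only with toxicity due to one drug.* Its interruption, resumption and 28-day rules are general; only its attribution rules are limited to one drug.

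**Conclusion.** The point holds for Table 6's permanent-stop rows. For a jointly attributed event that recovers, Table 4 restarts trametinib, Table 6 sets it at 0 mg for good, and no text decides between them. This assumes that the event is graded ≥3, recovers to Grade ≤1 without a delay of both drugs beyond 28 days, and is attributed to both drugs. Shared attribution is best supported for cardiomyopathy, which is documented for each drug. For RVO and ILD or pneumonitis the tables collide in the same way, but section 1.2.6.2 does not name either as an HCQ risk.

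The skin cross-reference is a plain slip. The second-occurrence difference (stop both drugs, or trametinib 1 mg) is a minor inconsistency for the sponsor to settle: Table 4 is the more cautious there, while section 3.1 favours continuing one agent, at PI discretion, when disease is controlled.

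This is a safety and consistency matter that should be corrected. It changes no sample size, power or decision threshold.

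**What to change.** Add to section 3.3: *When an event is attributed to both drugs or cannot be assigned to one, apply Table 4 to HCQ and Tables 5 and 6 to trametinib; the permanent-discontinuation rows of Table 6 override any restart of trametinib under Table 4.* In Table 4's skin row, change the reference from Table 5 to Table 6.

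As worded, the first clause would follow Tables 5 and 6 at a second Grade 3 event (HCQ stopped, trametinib 1 mg). If the sponsor wants Table 4's stop of both drugs to apply there, it should add that exception. The sentence settles trametinib only; the caution about HCQ in suspected cardiotoxicity stays as it is.

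The cost is one sentence and one corrected reference, with no added visits, tests or patients. The downside is that a few patients with shared-attribution events reduce or stop trametinib sooner. Imaging for the primary endpoint is kept: section 3.4 continues scans in patients who stop treatment without progression, until progression or 5 months.
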